#### Secondary endpoints:

- Differences in measures of mammographic density: i) visually assessed BIRADS, ii) Volpara and iii) predicted VAS using ‘for presentation’ and ‘for processing’ mammographic images and the relationship between these measures and 10-year and lifetime risk score in TCv8.

## 3. Analysis

The primary analysis will compare the risk categories and risk scores for the risk prediction models for women at entry to the clinic (or age 40) and at last follow-up in the clinic, and will compare the risk scores given by TCv8 and BOADICEA using different model inputs.

- i) **Change in risk categories** – NICE risk categories (average, moderate and high) will be compared by creating cross tabulations of risk categories at entry and at last follow-up – the number (and percentage) of women moving up and down risk categories will be

reported and the McNemar-Bowker test will be used to determine whether the change in risk categories is statistically significant between the two time points.

- ii) **Change in 10-year and lifetime risk scores** - change in continuous risk measures (10-year and lifetime risk estimates) will be estimated from TCv8 and BOADICEA risk prediction models. Normality and skewness of 10-year and lifetime breast cancer risk scores will be assessed. Where there is evidence of non-normality scores will be transformed. Scatterplots and correlation coefficients will be used to examine the relationship between 10-year and lifetime risk estimates at baseline and at latest follow-up.

Descriptive statistics will be used to report change in risk scores from time at entry to latest follow-up and will be compared using a paired t-test. Linear regression will be used to determine which risk factors (e.g. SNP313, MD) are associated with change in risk score.

- iii) **Comparison between risk models** - descriptive statistics will be used to report risk scores from TCv8 and the BOADICEA models and differences in risk scores compared. Models will be compared using a) classical risk factors alone, b) classical risk factors plus mammographic density, as measured by BIRADS, which can be included in both models and c) classical risk factors plus mammographic density and SNPs. Scatterplots and correlation coefficients will be used to examine the relationships between models and Bland-Altman plots used to show the agreement between the models.

Secondary analysis will focus on the comparison between differences in mammographic density measures and the relationship with risk scores using TCv8.

- iv) **Comparison of mammographic density methods and the relationship with TCv8 risk scores** – scatterplots, intraclass correlation coefficients and Bland-Altman plots will be used to look at the relationship between different mammographic density methods. Risk scores will also be compared for TCv8 using different methods for measuring mammographic density to determine the impact this has on overall risk score. Changes in NICE risk categories will be compared using the different methods using the McNemar-Bowker test and differences in the continuous risk measures will be compared using repeated measures analysis of variance (ANOVA).

- v) **Reader reproducibility for BIRADS** - reproducibility for readers assessing BIRADS score will be determined using inter-reader and intra-reader statistics, using the McNemar-Bowker test to assess agreement within and between readers.

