**Table 1. Nice categories of lifetime BC risk and subsequent management dependant on risk**

	Moderate risk (17-29%)	High risk (>30%)
Yearly screening	up to age 50	up to age 60
Chemoprevention	'consider'	'offer'
Risk reducing surgery	none	offer

\*Many referrals will be assessed at 'average' risk and returned to primary care

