### **Risk estimation models to be used to recalculate risk**

#### ***Calculation using Tyrer-Cuzick Version 8***

Phenotypic risk will be assessed using predicted remaining 10-year and lifetime risks to age 85 from the TC model V8 (Tyrer 2004; <http://www.ems-trials.org/riskevaluator/>). The following information from the original risk questionnaire collected before 2012 will be incorporated: age at baseline; first and second-degree relatives (age affected by breast and ovarian cancer or current age or age at death); age at first child, menarche and menopause; height and weight; and history of prior benign breast disease. Changes in these risk parameters will be assessed at subsequent clinical appointments and incorporated into the model.

Version 8 of the TC Model differs from V6 in that risk is estimated until the age of 85 (from 73 or 80 years) and because breast cancer risks have generally increased since V6 was developed (Tyrer et al., 2004). Thus, women will have in any case somewhat higher risks than previously given at their initial

appointment. However they still may end up with a lower risk estimate than originally given when MD and SNPs are taken into account (Brentnall et al., 2015).

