### ***Calculation using BOADICEA V – Can-Risk***

Collaborative work with the Cambridge team that have now produced a user-friendly risk algorithm called CanRisk from their BOADICEA programme, means we can now provide bespoke breast cancer 10-year and remaining lifetime risks especially for those who carry pathogenic variants in moderate risk genes CHEK2 and ATM that are not provided for in Tyrer-Cuzick model (Archer et al 2020). CanRisk includes the same inputs as Tyrer-Cuzick (above) but also includes additional genes. Women will be provided the CanRisk output instead of Tyrer-Cuzick when they carry a pathogenic variant in any of the high or moderate risk genes. Comparisons will also be made to identify discrepancies in 10-year risks that would mean women were in different risk categories.

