### **Statistical Analysis Plan**

The baseline anthropometric, familial and hormonal information from the FHRPC questionnaires will be entered into the breast cancer risk prediction models under consideration (TCv8 and CanRisk) and estimates of absolute 10 year and lifetime risk to age 80 risk obtained for each woman. The performance of the models will be compared in two ways; differences in prediction of individual risk and the change in category of risk (average, moderate and high) according to NICE guidelines. The follow-up period will be taken to be the time from initial referral and first clinic assessment with risk assessment to the most recent assessment or December 1st 2020, whichever is later

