### 3.4 Part 2: Exploring the experience of receiving updated breast cancer risk estimates in women with a family history of breast cancer: an interview study

#### Participants and recruitment

Twenty women who have consented to discuss their re-evaluated risk estimate at the FHRPC (see part 1) and who have consented to be contacted about future research (namely the related interview studies in part 2 and 3) will be invited to participate in a semi-structured interview (over the telephone or via Zoom). Purposive sampling will be used to invite 20 women who have had their breast cancer risk estimate re-evaluated by the clinical team. The research team will invite 10 women who have a re-evaluated risk that has either increased by at least one category and 10 women who have decreased by at least one category. Eligibility screening will be conducted before sending invitation letters by the breast cancer research team at MFT or by an eligible member of the research team with the requisite permissions. We estimate that a sample size of 20 will be sufficient to explore views around re-evaluated risk estimate experiences from the perspective of women who have received a range of risk estimate changes.

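### The entry versus last-follow-up table of NICE categories mixes ageing with the effect of the new risk factors, because remaining lifetime risk is judged against fixed lifetime cut-offs at two different ages

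*Combined protocol and SAP*

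**What the plan says.** Section 3.1, Statistical Analysis Plan, Analysis item i, compares NICE categories by "creating cross tabulations of risk categories at entry and at last follow-up". It reports the number and percentage of women moving up and down and tests the change between the two time points. The opening sentence of that section gives the first time point as entry to the clinic, or age 40, without defining when age 40 applies. Item ii compares 10-year and lifetime scores at the two times with a paired t-test, then regresses the change on risk factors. It names SNP313 and density as examples, and no age or interval term.

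The scale of these risks is set out earlier in Section 3.1. For Tyrer-Cuzick the plan will use "predicted remaining 10-year and lifetime risks to age 85 from the TC model V8"; for CanRisk it speaks of "bespoke breast cancer 10-year and remaining lifetime risks". The cut-offs come from Table 1 in Section 1.2, headed "Nice categories of lifetime BC risk and subsequent management dependant on risk": 17-29% for moderate and 30% for high, one set for all ages.

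Primary objective vii in the SAP is the change in NICE category when new risk factors are added to standard models. Objective viii is the change between first referral and latest visit. Item iii varies the inputs (classical; plus density; plus density and SNPs), but for risk scores compared between models, not for categories.

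**The concern.** Remaining lifetime risk counts only the years still ahead. A woman who reaches 50 without cancer has used up part of the risk she carried at 40, so her figure is lower even if nothing about her has changed. Setting both figures against the same 17% and 30% lines builds a downward drift into the two-date table.

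Objective vii asks a different question: what the added factors do to the category. No listed analysis tabulates categories with and without those factors at one age, so item i is the table a reader would use to answer it. Downward moves would then combine ageing, updated classical factors and the new information, with no way to tell them apart. The paired t-test on lifetime risk in item ii carries the same drift, and its regression could leave differences in elapsed time unexplained. Section 1.1 expects the results to inform the next NICE guidance, so what the counts mean matters.

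**Working it through.** **Any figure to reproduce.** The plan states no expected shift for this analysis. The nearest figure is the pilot in Section 1.2: 53, 40 and 13 of 106 women moved down, stayed or moved up. 53/106 = 50%, 40/106 = 38% and 13/106 = 12%, as stated. That contrast was Tyrer-Cuzick with density and SNPs against Tyrer-Cuzick without them.

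**Formula.** Let R(a) be remaining lifetime risk at age a. With all inputs other than age fixed and the same end age, R(b) = 1 - (1 - R(a))^s, where s is the share of the cumulative hazard from a to the end age that still lies ahead at b. Since s is below 1 for any later age, R(b) is always below R(a). The size depends on the hazard shape. The documents give no age-specific incidence, so the shapes below are assumptions. Competing mortality is ignored.

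**Illustration from age 40, end age 85.** Two shapes: flat, and rising linearly to double between 40 and 65, then flat.
- At 50: s = 35/45 = 0.778 (flat) or 65.5/77.5 = 0.845 (rising). 30% becomes 1 - 0.70^0.778 = 24.2%, or 1 - 0.70^0.845 = 26.0%.
- At 55: s = 30/45 = 0.667 or 58/77.5 = 0.748. 30% becomes 21.2% or 23.4%; 20% becomes 13.8% or 15.4%.
- Entry risk needed to be still at 30% at 55: 1 - 0.70^(1/s) = 41.4% or 37.9%. To be still at 17%: 24.4% or 22.0%.

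**Wider range.** Four shapes: constant; linear rise from age 20; rise from 20 to 50 then flat; constant to 60 then halved. End age 85.
- 8-year gap, entry age 30 to 45: 30% becomes 22.3-28.6%, a fall of 1.4 to 7.7 points. The smallest fall is the linear rise from 30 to 38 (s = 0.946); the largest is the halved shape from 45 to 53 (s = 19.5/27.5 = 0.709). Entry risk needed to stay high: 31.4-39.5%.
- 20-year gap (30 to 50, 40 to 60): 30% becomes 12.8-25.0%. Entry risk needed to stay high: 35.8-60.4%.

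**How long the gap is.** Entry was about 2000 to 2012. The SAP introduction ends follow-up at the latest assessment or 1 December 2020, whichever is later, which implies roughly 8 to 21 years. The density section instead uses the last clinic mammogram at discharge, or the last visit if still under review. SAP Methods uses the latest clinic appointment, and Analysis the last follow-up in the clinic. About 271 of 954 women were still under follow-up in October 2020, so for about 683 (72%) these definitions may give different, shorter gaps.

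**Horizon.** The SAP introduction specifies "estimates of absolute 10 year and lifetime risk to age 80 risk obtained for each woman", while the Tyrer-Cuzick section uses 85. At either age the fall occurs, provided the same one is used at both dates.

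**What cannot be computed.** The distribution of risk at entry is not given, so neither the number of women who would cross a line through ageing nor the bias in the reported percentages can be derived.

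**The case against.** Several points on the other side have force.

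- Change between first referral and latest visit is itself a stated objective (viii), and item i claims only to test change between two time points. That stands: the two-date table is legitimate for objective viii. It does not answer objective vii.
- Same-age estimates are already in the plan. Section 1.1 says risk will be estimated retrospectively at entry as well as at latest follow-up, a mammogram near first referral will be read, and item iii reruns scores on three input sets. This stands too. The gap is that none of it reaches the category table.
- The scale that sets the category is not settled. The primary endpoints link NICE categories to 10-year as well as lifetime risk, and 10-year risk need not fall. Scaled to 30% lifetime risk at 35, it goes from 5.0% at 35 to 6.8% at 43 under the rise-to-50 shape. No 10-year cut-offs are given, so the SAP must say which scale applies.
- A reader might infer that Parts 2 and 3 will place women in the decreased group merely because they aged. The documents do not support that. Those groups, for example "10 women who have a re-evaluated risk that has either increased by at least one category", are defined against the estimate women were first given, from modified Claus or early Tyrer-Cuzick. Section 3.1 notes that version 8 runs to 85 rather than 73 or 80 and tends to give higher risks. With that change of horizon, 30% at 35 becomes 26.0-32.3% at 43 (80 to 85) or 28.4-40.0% (73 to 85), so the ageing fall can be fully offset. Those parts also study the estimate women actually received.
- Running last-follow-up inputs from the entry age would remove ageing, but it can be incoherent: a later menopause or a density read at 55 would be assigned to a 40-year-old. The remedy should avoid this.

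**Conclusion.** The point holds for SAP items i and ii where the category or score is remaining lifetime risk from the same model to the same horizon. Women within a margin above 17% or 30% can fall a category through ageing alone, and the planned table cannot separate this from the new-factor effect in objective vii. The direction is certain under those conditions. The size rests on assumed hazards: for a woman at 30%, about 1 to 8 points over 8 years and about 5 to 17 points over 20 years. Women well above a cut-off keep their category, particularly over the shorter gap.

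It would go too far to say that all women drop, that the gap is always 8 to 20 years, or that the downward moves seen will be mainly ageing. The pilot found half of its women moving down in a with-and-without comparison, so many decreases are expected without any ageing effect. Nor does the point extend to the Parts 2 and 3 groupings. The undefined age-40 option does not remove the problem, since it touches only the first time point.

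**What to change.** 1. For objective vii, make the primary category table, with its McNemar-Bowker test, a comparison of NICE category with and without the new factors: classical; plus density; plus density and SNPs; plus gene results where the model accepts them. Each comparison uses the same date, start age and horizon. Do it at entry and, separately, at last follow-up. Ageing then contributes nothing, by construction, and no later measurement is put on an earlier age.
2. Keep the entry versus last-follow-up table for objective viii, labelled as change in remaining risk that includes ageing. Label the item ii paired comparison in the same way, and include age at entry and interval in the item ii regression.
3. Name the risk scale that sets the category. Reconcile the horizon (80 in the SAP introduction, 85 in the Tyrer-Cuzick section) and the follow-up date across the SAP and the density section. Define when age 40 replaces entry.
4. Leave the Parts 2 and 3 groups tied to the estimate women received.

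Cost: SAP wording and extra tabulation, mainly from model runs already planned. The three input sets in item iii must be run at both dates, which the SAP does not say outright, and gene results are not listed there as a separate set, so a further run may be needed. The downside is that the research table may differ from the change in remaining risk quoted in clinic, so both must be clearly labelled.

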#### **1. Objectives**

Primary

- vii) To determine change in NICE categories of risk (average, moderate and high risk) when new risk factors are added to standard breast cancer risk models.

- viii) To explore how much new risk models (including MD, SNP313 and mutation testing) change risk estimates previously communicated to women in the FH-Risk study, between their first referral and their latest visit to the FHRPC
- ix) To compare 10-year and lifetime risk estimates given by Tyrer-Cuzick (v8) and the BOADICEA model (v5) (Can-Risk)

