#### Primary endpoints:

- 10-year and lifetime breast cancer risk and the corresponding NICE risk categories for two risk prediction models: i) TCv8 and ii) BOADICEA v5.
- Risk scores from TCv8 and BOADICEA will be assessed using different model inputs: i) classical factors alone, ii) classical factors plus mammographic density (BIRADS) and iii) classical factors plus mammographic density plus SNPs.

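### The first primary objective asks how NICE category changes when new factors are added, but no listed analysis compares categories with and without those factors in the same model at the same date

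*Combined protocol and SAP*

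**What the plan says.** SAP section 1 (Objectives) lists as its first primary objective, vii, the "change in NICE categories of risk (average, moderate and high risk) when new risk factors are added to standard breast cancer risk models". Objective viii is separate and concerns change between first referral and latest visit.

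Under Primary endpoints in section 2, one bullet names 10-year and lifetime risk with the NICE categories for the two models. A second bullet carries the input sets, for scores: "Risk scores from TCv8 and BOADICEA will be assessed using different model inputs: i) classical factors alone", then with BIRADS density added, then with density and SNPs.

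Section 3 opens by saying that the primary analysis compares categories and scores "for women at entry to the clinic (or age 40) and at last follow-up in the clinic". The rest of that sentence turns to scores only, saying that the analysis "will compare the risk scores given by TCv8 and BOADICEA using different model inputs". Item i then cross-tabulates category at entry against category at last follow-up, and "the McNemar-Bowker test will be used to determine whether the change in risk categories is statistically significant between the two time points". It does not name the model version or inputs for either margin.

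Item iii uses the three input sets, but to set one model against the other: "descriptive statistics will be used to report risk scores from TCv8 and the BOADICEA models and differences in risk scores compared". Item iv does compare categories inside TCv8, but as a secondary analysis across density methods: "Changes in NICE risk categories will be compared using the different methods using the McNemar-Bowker test". Outside the SAP, the CanRisk subsection of 3.1 says "Comparisons will also be made to identify discrepancies in 10-year risks that would mean women were in different risk categories", which is again model against model.

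**The concern.** Objective vii is a with-versus-without question, while item i answers a then-versus-now question. A woman's category can differ between entry and last follow-up for reasons unrelated to density or SNPs:

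- **Ageing.** Both models report remaining risk (section 3.1, Tyrer-Cuzick and CanRisk subsections).
- **Updated inputs.** Changed risk factors are fed into the model at later appointments (Tyrer-Cuzick subsection).
- **Re-measured density.** Mammograms are read near first referral and again at discharge or last visit (Estimation of Mammographic Density).

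The protocol asks whether NICE guidelines should change to include the new models (1.2 and 1.3) and expects to inform their next iteration (1.1). As written, the headline percentages moving up and down, and their p-value, could not be read as the effect of adding density and SNPs. With the contrast unspecified, the model, date, horizon and input set for objective vii could also be chosen after results are seen.

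**Working it through.** **Step 1. The one with-versus-without result in the documents.** The pilot (section 1.2) compared Tyrer-Cuzick with density and SNP18 against Tyrer-Cuzick alone in 106 women. Down: 53/106 = 50.0%. Unchanged: 40/106 = 37.7%. Up: 13/106 = 12.3%. These match the stated 50, 38 and 12%. This is the type of contrast objective vii needs.

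**Step 2. Section 3, item by item.**

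| Item | Outcome | Contrast | Answers vii? |
|---|---|---|---|
| i | NICE category | Entry vs last follow-up; inputs not stated | No |
| ii | Continuous score | Entry vs last follow-up; regression of the change on factors such as SNP313 and density | No |
| iii | Continuous score | TCv8 vs BOADICEA within each input set | No |
| iv | Density measures; TCv8 category and score | BIRADS vs Volpara vs predicted VAS; every arm includes density, no SNP contrast; secondary | No |
| v | BIRADS grade | Within and between readers | No |

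None of the five makes the comparison.

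**Step 3. How far ageing alone could move item i (illustration).** Assumptions, not taken from the documents unless marked:

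- Same model, inputs and horizon at both times. The horizon is 80 (SAP opening paragraph) or 85 (Tyrer-Cuzick subsection).
- Hazard from entry age to the horizon is flat, or rises linearly 2- or 3-fold.
- Category cuts at 17% and 30% lifetime risk (Table 1).
- Entry risk is lognormal, log-SD 0.30, median 25% or 30%, truncated at 17%. About 30% or 51% of women are then high risk; section 1.2 gives 49.7% for the clinic.

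Remaining risk at age a is 1 − (1 − L)^f. L is lifetime risk at entry and f is the share of cumulative hazard still ahead. For L = 32% at age 40, assessed again at 50:

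- Flat hazard, horizon 80: f = 30/40 = 0.75, so risk = 1 − 0.68^0.75 = 25.1%.
- 3-fold rise, horizon 85: f = 0.864, so risk = 1 − 0.68^0.864 = 28.3%.

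A high-risk woman becomes moderate-risk with nothing new known about her. Share of women moving down a category:

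| Entry age | 5 years | 8 years | 10 years |
|---|---|---|---|
| 40 | 9–22% | 15–36% | 20–47% |
| 30 | 7–17% | 12–28% | 16–36% |

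Log-SD 0.20 or 0.40 changes the range for entry at 40 and 10 years only to 20–44% or 19–46%. No woman moves up, because remaining lifetime risk can only fall when nothing else changes.

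**Step 4. Effect on the test.** The McNemar-Bowker statistic is Σ(b − c)²/(b + c). With moves in one direction only, every c is 0 and the statistic equals the number of movers. The smallest case in the grid is 6.9%:

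- 271 women (those still in follow-up): 18.7, rounded down to 18. Chi-square 18 on 3 df, p = 0.0004.
- 954 women (the full cohort): 65.8, rounded down to 65, p < 0.0001.

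Item i's analysis set is women with two risk appointments and scores. Its size is not stated, so these two numbers serve only as reference sizes.

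**Step 5. Precision of the missing table (Wilson 95% intervals, if pilot rates held).** At n = 954, 50% down has 46.8–53.2% and 12% up has 10.0–14.2%. At n = 271, in whole women, 136 down has 44.3–56.1% and 33 up has 8.8–16.6%. The pilot used SNP18 and the study uses SNP313, so the rates may differ.

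**The case against.** The strongest reply is that item i could be run once per input set. Both models are to be scored under three sets, and the abstract (1.1) says risk is estimated retrospectively at entry and at latest follow-up. The entry margins would then show the category distribution with and without the new factors at one date. This is a fair reading of what could be done, but margins give only net shifts. They do not show how many women moved up and how many down, and no test of that contrast is planned.

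A second reply is that the abstract defines the quantity as risk given at entry against re-estimated risk, so a change of base model belongs to the question. That suits the question about previously communicated risk. Objective vii is worded separately, about adding factors to standard models, and the pilot analysed it that way. Risk given at entry came from modified Claus or Tyrer-Cuzick, so this comparison changes more than the new inputs. Item ii's regression links SNP313 and density to change, but in score over time, not in category.

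Two limits on the illustration stand. Its risk distribution and hazard shapes are assumed. It also covers lifetime categories only: 10-year risk need not fall with age. With the 3-fold hazard and horizon 80, the woman at 32% has a 10-year risk of 5.8% at 40 and 8.1% at 50. Ageing still confounds that measure, but in the opposite direction.

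**Conclusion.** The concern holds. The first-listed primary objective has no matching analysis, and the one primary category table and test cannot stand in for it under any reading of its inputs. This follows from the text alone and does not depend on the illustration.

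The illustration indicates scale: ageing alone could move roughly 7–22% of women down a lifetime category in 5 years and 16–47% in 10, across entry ages 30 to 40. That is enough to make item i significant with no new factor involved. It assumes constant inputs and horizon, the hazard shapes above and an assumed entry-risk distribution. It does not quantify updated classical inputs and does not forecast the study's result. The concept and the scores are already in the plan; what is missing is the paired category comparison. It should be added before analysis.

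**What to change.** Add to SAP section 3, as the analysis for objective vii, cross-tabulations of NICE category within TCv8 and separately within BOADICEA. Use one fixed date and horizon, for example clinic entry with the mammogram nearest first referral. Compare classical factors with classical plus density, and classical with classical plus density plus SNP313. Report the number and percentage moving up and down with 95% confidence intervals, and the McNemar-Bowker test. State whether gene-panel results count as a new factor here, since the Primary endpoints input sets omit them.

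Keep entry versus last follow-up for objective viii. For that table, state the risk estimate, model version, inputs and horizon at each time, and say when age 40 replaces entry. Reconcile the lifetime horizon of 80 in the SAP's opening paragraph with 85 in the Tyrer-Cuzick subsection. State that the total change over time will not be attributed to the new factors. Splitting it into ageing and new-factor parts is optional.

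The cost is SAP wording plus some extra model runs and tables on scores and data already planned or held. No new participants or measurements are needed.
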